**Version Date: 06/26/2019**

## Resuscitation with Plasma in Patients with Septic Shock

**Summary:** There is a knowledge gap regarding the optimal initial fluid to achieve effective resuscitation and improved outcomes in septic shock. Shock-induced endotheliopathy (SHINE) may be an underlying pathologic mechanism for worsened outcomes in septic shock and a potential therapeutic target that can be modulated by resuscitation fluids. This project proposes a pilot randomized controlled trial to address this knowledge gap by evaluating plasma as a potential novel strategy to mitigate SHINE and improve clinical outcomes.

### Background:

Sepsis and septic shock are a major worldwide public health problem. Although implementation of the evidence-based Surviving Sepsis Guidelines has resulted in improvement in sepsis-related deaths, in-hospital mortality continues to range from 12-40%. The guidelines provide strong recommendations for initial resuscitation with crystalloids – 30 mL/kg within the first 3 hours. However, the guidelines state that there is “little available evidence from RCTs to support its practice; this is an area in which research is urgently needed”. Randomized trials have primarily compared crystalloids to colloids and have not evaluated the recommended fluid volume. Furthermore, there is observational data from large administrative databases that increased fluid administration in the first 24 hours increases mortality.

**Figure 1:** Conceptual model of how septic shock leads to sympathoadrenal activation, inflammation, and ischemia, which affects the endothelial glycocalyx, endothelial permeability, and hemostatic balance, resulting in edema and microcirculatory disturbances that cause organ dysfunction

Abbreviations: sTM = soluble thrombomodulin; sFLT-1 = soluble fms-like tyrosine kinase-1; VEGF = vascular endothelial growth factor; sRAGE = soluble receptor for advanced glycation endproduct; HMGB-1 = high mobility group protein-1; IL = interleukin; vWF = von Willebrand factor; tPA = tissue plasminogen activator; NE = norepinephrine; rTEG = rapid thromboelastogram

\*indicates biomarkers that belong to more than 1 category

Recently, shock-induced endotheliopathy (**SHINE**) has been proposed as a shared pathophysiologic mechanism associated with worsened outcomes in patients with critical illness including trauma and sepsis. Activation of the sympathoadrenal system and release of catecholamines due to acute injury (i.e., sepsis or trauma) leads to breakdown of the glycocalyx, or the network of membrane-bound proteoglycans and glycoproteins that covers the endothelium (**Figure 1**). This has been associated with capillary leakage and microvascular thrombosis, ultimately resulting in organ dysfunction and increased mortality. Research suggests that

endotheliopathy is both a marker and a driver of worsened outcome. Thus, interventions to prevent, mitigate, or treat SHINE may improve outcomes in patients with shock. SHINE biomarkers, such as syndecan-1, interleukin-6 (IL-6), and soluble fms-like tyrosine kinase (sFLT-1), have been shown to correlate with clinical outcomes in septic patients.

Resuscitation of shock patients with plasma shows promise as a novel resuscitative strategy. Specifically, plasma may improve outcomes by modulating SHINE as measured by biomarkers of glycocalyx damage (i.e., syndecan-1), and endothelial injury (i.e., sFLT-1, VEGF, sTM). Resuscitation with plasma as the primary volume expander in trauma patients have been associated with a reduction in serum biomarkers of endotheliopathy, improved survival, and decreased morbidity associated with inflammatory and edema-related complications such as acute lung injury and abdominal compartment syndrome. Animal models of sepsis and a prospective sub-study of a randomized, controlled trial (RCT), have shown that resuscitation with plasma is associated with decreased levels of syndecan-1, which may reflect restoration of endothelial integrity, although the underlying mechanism is unknown. Plasma resuscitation in a rat model of sepsis demonstrated attenuation of inflammatory markers, endothelial injury, and catecholamines; significantly reduced pulmonary edema as measured by wet-to-dry weight ratios; and improved 48-hour survival as compared to normal saline. However, although these studies suggest that plasma may be a promising therapy in septic shock, there have been no human RCTs. Furthermore, there have been no studies establishing causation between SHINE and outcome.

### **Hypothesis and Specific Aims:**

**Hypothesis:** We hypothesize that among patients with septic shock, initial resuscitation with plasma versus balanced crystalloids will decrease biomarkers of endotheliopathy, improve patient outcomes (such as decrease number of ICU-free days, decreased morbidity associated with end-organ damage), and reduce in-hospital all-cause mortality. We propose to perform a pilot RCT to test this hypothesis using the following specific aims:

**Specific Aim 1:** To evaluate the effects of plasma versus balanced crystalloids on serum markers of glycocalyx breakdown, endothelial leakage, inflammation, hemostasis, sympathy-adrenal activation, and degree of coagulopathy (using rapid thromboelastography parameters) **[Figure 1]**.

**Specific Aim 2:** To evaluate differences in total volume of fluids needed to resuscitate patients in the plasma group versus crystalloids group during the initial 24 hours of resuscitation.

**Specific Aim 3:** To determine the effect of plasma resuscitation on organ dysfunction, ventilator-free days, intensive care unit (ICU) free days, hospital length of stay, mortality, and adverse events.

[figure not shown]

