#### **Informed Consent:**

Exception from Informed Consent will not be used in this trial. Written informed consent will be obtained from potential subjects or a legally authorized representative prior to randomization.

**Randomization:** Randomization will occur once the informed consent has been obtained. A 1:1 allocation will be used for the randomization. Subjects will be randomized to either the intervention arm (use of plasma) or the control arm (standard of care). Randomization will be performed using a computer-generated random sequence placed in opaque, consecutively-numbered, sealed envelopes kept in the locked Center for Translational Injury Research (CeTIR) office. A CeTIR research coordinator is available 24 hours a day, 7 days a week. Allocation will be 1:1. Patients will be stratified by enrollment location (STICU, ED, and Medical) in 5 blocks of 4 and 1 block of 6 for a total of 26 patients. **[Figure 4].**

**Figure 4** – Flow diagram depicting patient screening, enrollment, and randomization.

**Intervention:** Initial resuscitation with plasma will be 10 mL/kg (700 mL in a typical 70 kg adult). Traditional doses of plasma, when used to correct coagulopathy range from 10-15 mL/kg. The plasma will be administered at a rate of 2-3 mL/kg/hr (140-210 mL/hr in a typical 70 kg adult). A research physician will be at bedside to follow patient resuscitation. Plasma administration may be terminated before the entire dose is administered if patients show clinical improvement, or if the treating clinician has concerns about circulatory overload. After the initial dose of plasma has

been given, subsequent fluid resuscitation (crystalloid or colloid) will be given at the discretion of the treating clinician.

The blood bank will have thawed plasma available on call as soon as an eligible patient has been identified. Type and screen will be performed concurrently to provide donor-matched plasma for subjects randomized to intervention group. For patients who proceed to the operating room during fluid resuscitation, the anesthesiology team will continue fluid administration per study protocol.

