**Control:** Usual care using balanced crystalloids (Iso-Lyte or Plasma-Lyte) only will follow Surviving Sepsis Campaign guidelines. Controls will receive 30 mL/kg (2100 mL in a typical 70 kg adult) of crystalloids within the first 3 hours. Crystalloid administration may be terminated before the entire dose has been administered if patients show clinical improvement, or if the treating clinician has concerns about circulatory overload. After the initial dose of crystalloids has been given, subsequent fluid resuscitation (crystalloid or colloid) will be given at the discretion of the treating clinician.

**Observational Arm:** Patients with suspected sepsis who do not meet the criteria for randomization or unable to obtain informed consent in a timely fashion (within 3 hours of research team being notified) will be enrolled in a prospective observational arm of the study. Baseline demographic and hospitalization data including the fluid therapy per the attending physician's discretion will be collected. Blood samples will also be collected at 0, 2, 3, 6, 12, and 24 hours upon determination of patients' eligibility for the observational study arm. A waiver of informed consent will be requested given that no intervention will be performed on the patient and that the study will be at minimal risk to the patient. The research team will attempt to obtain written informed consent from the patient or his/her legal authorized representative for 24 hours after patient enrollment into the observational study arm. If informed consent is denied by the patient or his/her legal authorized representative, no further data or blood samples will be collected and any data or blood samples collected prior to decline of participation will not be used in this study.

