**Endpoints of Resuscitation:** Fluid resuscitation in both the intervention and the control arms will be titrated to serial reassessments of the patient's volume status via blood pressure monitoring (MAP > 65 mmHg), urine output measurements (goal of  $\geq 0.5$  cc/kg/hr), CVP measurements (>8 mmHg), stroke-volume variation on hemodynamic monitors (such as the Vigileo), inferior vena cava (IVC) collapsibility index via bedside ultrasound, and lactate clearance (goal of  $\geq 50\%$  clearance after 6 hours of resuscitation). Serial laboratory examinations including lactate levels will be performed per standard of care in the ICU, until the lactate has normalized. Additional fluid support after the initial plasma or crystalloid bolus will be given at the discretion of the treating clinician, keeping in mind that septic shock patients in several randomized trials required 6-8L crystalloid per day.

**Co-interventions:** Both groups will receive standard care following Surviving Sepsis Guidelines, including procurement of blood cultures, administration of broad-spectrum antibiotics, transfusion of packed red blood cells for hemoglobin < 7 mg/dL, and use of vasopressors to maintain MAP > 65 mmHg.

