## Appendix A: List of Data Elements

### Demographics

- Age
- Gender
- Race
- Ethnicity
- Height/Weight/BMI

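### Aim 2 compares total fluid in mL without adjusting for body weight, although the initial doses are per kg; at 13 per arm this adds avoidable noise

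*Combined protocol and SAP*

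**What the plan says.** Specific Aim 2 is worded as a volume comparison: "To evaluate differences in total volume of fluids needed to resuscitate patients in the plasma group versus crystalloids group", over the first 24 hours. No per-kg scale is attached.

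The initial doses are per kg. Under Intervention: "Initial resuscitation with plasma will be 10 mL/kg (700 mL in a typical 70 kg adult". Under Control: "Controls will receive 30 mL/kg (2100 mL in a typical 70 kg adult) of crystalloids within the first 3 hours". Either may be stopped early. After the initial dose, in both arms, "subsequent fluid resuscitation (crystalloid or colloid) will be given at the discretion of the treating clinician". Endpoints of Resuscitation sets a urine-output goal per kg per hour. It also notes, in litres, that "septic shock patients in several randomized trials required 6-8L crystalloid per day".

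Randomization is 1:1, stratified by enrolment location only, and Sample Size gives 13 patients per arm. For continuous outcomes, Statistical Analysis specifies a mixed model with terms for treatment arm and period plus a patient-level random effect. Weight is not named there, but Appendix A lists it among the baseline data ("Height/Weight/BMI").

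**The concern.** When a dose is fixed per kg, a heavier patient receives more millilitres for reasons unrelated to the treatment comparison. With 13 patients per arm, mean weights can differ between arms by several kilograms by chance, and part of that difference then appears as a difference in fluid volume.

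The random subject effect does not help. A 24-hour total is one value per patient, so the effect cannot separate weight from the rest of the between-patient variation.

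At stake is the precision of the Aim 2 estimate. The pilot is meant to supply estimates for a larger trial. The initial doses already impose a volume gap between arms, so the useful information is whether later fluid narrows or widens it. A few tenths of a litre of removable noise matters for that question.

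**Working it through.** **Inputs from the protocol.** Initial doses 10 and 30 mL/kg (Intervention, Control); 13 per arm (Sample Size); 70 kg typical adult; 6-8 L crystalloid per day (Endpoints of Resuscitation).

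**Assumption.** The protocol gives no weight SD. I take 20 kg and show 15-25 kg.

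**1. The plan's own figures.** 10 × 70 = 700 mL and 30 × 70 = 2100 mL, as stated. The difference is 1400 mL, or 20 mL/kg. This is the only volume contrast that can be derived. The protocol states none for the 24-hour total.

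**2. Chance difference in mean weight.** SE = SD × √(2/13).
- SD 20: 20 × 0.392 = 7.84 kg; 95% limit 1.96 × 7.84 = 15.4 kg.
- SD 15 and 25: SE 5.88 and 9.81 kg; 95% limits 11.5 and 19.2 kg.

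**3. Only the initial doses scale with weight.** The initial-dose gap is 30 × (mean control weight) − 10 × (mean plasma weight). Its 95% half-width is 1.96 × SD × √((30² + 10²)/13).
- SD 20: 1.96 × 20 × √(1000/13) = 344 mL.
- SD 15 and 25: 258 and 430 mL.

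At SD 20 kg the initial-dose gap is thus 1400 ± 344 mL. The noise is about a quarter of the gap (344/1400 = 25%).

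**4. All 24-hour fluid scales with weight.** The middle of 6-8 L is 7 L; 7000/70 = 100 mL/kg in both arms.
- SD 20: 1.96 × 7.84 × 100 ≈ 1540 mL.
- SD 15 and 25: about 1150 and 1920 mL.

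This is an upper case that rests on an assumption the protocol does not make.

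**5. What adjustment would remove in step 3.** With a common weight slope of about 20 mL/kg (the average of 10 and 30), the adjusted gap is (30·Wc − 10·Wp) − 20·(Wc − Wp) = 10·(Wc + Wp), where Wc and Wp are the mean weights in the control and plasma arms. The difference in weight between arms drops out. The part removed is 20 × 15.4 = 308 mL at the 95% limit. What remains depends only on the overall mean weight of the 26 patients: 1.96 × 20 × 20/√26 = 154 mL. As a check, √(308² + 154²) = 344.

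| Assumed weight SD | Only initial doses scale | All 24-hour fluid scales |
|---|---|---|
| 15 kg | ±0.26 L | ±1.2 L |
| 20 kg | ±0.34 L | ±1.5 L |
| 25 kg | ±0.43 L | ±1.9 L |

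**The case against.** A reader might infer that chance weight imbalance can produce a volume gap as large as the 1.4 L initial difference. The per-kg doses do not support this. Even at 30 mL/kg, weight alone would need mean weights 1400/30 = 46.7 kg apart, about 6 standard errors at SD 20 kg. The ±1.5 L figure requires later fluid to be proportional to weight. The protocol leaves that fluid to the clinician, and the daily figure is in litres. Urine output is the only per-kg target; arterial pressure, CVP, stroke-volume variation, IVC collapsibility and lactate clearance are not. The result is also sensitive to mean weight. At 80 kg, 7 L is 87.5 mL/kg, so the limit is 15.4 × 87.5 ≈ 1.35 L against an initial gap of 20 × 80 = 1.6 L. All of this stands.

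A reader might also infer a bias towards apparent fluid sparing with plasma. That does not follow either. A heavier plasma arm is as likely as a heavier control arm, and the planned 95% intervals already carry this scatter. The absence of stratification by weight is not a defect in a 26-patient pilot already stratified by location.

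Making mL/kg the main scale is not clearly better. If mL/kg is independent of weight (weight CV 25%, mL/kg CV 30-50%, both assumed), the relative variance in mL is 1.3-1.8 times that in mL/kg: ((1 + v²)(1 + w²) − 1)/v², with v the mL/kg CV and w the weight CV. If later litres are unrelated to weight, dividing by weight brings a penalty of similar size the other way. Total volume is also a legitimate quantity and matches the outcome in the rat experiment under Preliminary Data.

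Finally, the opening of the secondary-outcomes paragraph after Table 2 was missing from the text reviewed, so a per-kg definition there cannot be excluded. Aim 2 and the Statistical Analysis section are intact and contain none.

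**Conclusion.** The point holds as a modest precision issue. Aim 2 is in total volume, the initial doses are per kg, and the stated model omits a recorded baseline variable that must drive part of the outcome. At an assumed weight SD of 20 kg (15-25), the resulting noise in the arm difference is about ±0.34 L (0.26-0.43 L) at the 95% limit if the full initial doses are given and only they scale with weight. It rises towards ±1.5 L (1.2-1.9 L) only to the extent that later fluid also scales with weight, on which the documents are silent. The estimate remains unbiased and its interval valid. Nothing here threatens the trial.

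**What to change.** Keep total 24-hour volume in mL as the Aim 2 outcome. In Statistical Analysis, add a sentence stating that the model for this outcome includes enrolment weight as a covariate. Report mL/kg by arm as a supplementary summary.

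No new data are needed and no treatment rule changes. The cost is one degree of freedom: for a single 24-hour total in 26 patients, residual degrees of freedom fall from 26 − 2 = 24 to 26 − 3 = 23. If later fluid proves unrelated to weight, the adjustment gains little or nothing.

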### **Significance:**

This will be the first randomized trial comparing plasma, which has been demonstrated to have beneficial effects in animal models and in other types of shock, to usual care or balanced crystalloids. Furthermore, this study will provide insights regarding the mechanism by which fluids can influence outcomes in septic shock.

[figure not shown]
### **Preliminary Data:**

Plasma Resuscitation in Rat Model of Septic Shock - We randomized rats who underwent cecal ligation and puncture to resuscitation with plasma (n = 14), normal saline (n = 11), and sham (n = 5). Resuscitation with plasma as determined by lactic acid clearance attenuated inflammatory markers (interleukin-6) **[Figure 2]**, glycocalyx shedding (syndecan-1) **[Figure 3]**, and

catecholamines (norepinephrine). Plasma significantly reduced pulmonary wet-to-dry weight ratios, increased mean arterial pressures (MAPs), reduced volume of total fluids administered, and improved 48-hour survival.

**Figure 2** – Significant decrease in serum IL-6 in septic rats resuscitation with plasma as compared to normal saline.

**Figure 3** – Significant decrease in serum syndecan-1 in septic rats resuscitation with plasma as compared to normal saline.

### **Study Design & Methods:**

The proposed trial is a pilot, efficacy, single-center RCT comparing initial plasma to balanced crystalloid resuscitation in surgical patients with septic shock. The trial will investigate modulation of SHINE as a strategy by which outcomes in shock patients may be improved. The trial will follow the Consolidated Standards in Reporting of Trials (CONSORT) guidelines and has been registered on ClinicalTrials.gov (NCT03366220).

**Setting:** The study will take place at Memorial Hermann Hospital – Texas Medical Center (MHH-TMC), a Level I trauma and tertiary care center located in Houston, Texas.

**Study population:** The target population includes critically ill (including medical patients), traumatically-injured or surgical patients who have sepsis, hypotension with MAP < 65 mmHg, and signs of hypoperfusion such as lactic acid > 2.2 mmol/L, altered mental status or decreased urine output (< 0.5 mL/kg in the past hour).

### **Inclusion Criteria:**

Patients meeting the following criteria will be enrolled:

- $\geq 18$  years old and
- Have a Sepsis Screening Score (SSS)  $\geq 4$  with a suspected source of infection (**Table 1**)
- Written informed consent obtained

Patients meeting any of the following criteria will be randomized:

- Hypotension with MAP < 65 mmHg
- Lactic acid > 2.2 mmol/L,
- Altered mental status
- Decreased urine output of < 0.5 mL/kg in the past hour.

	0	1	2	3	4
Heart rate	70 – 109		55 – 69 110 – 139	40 – 54 140 – 179	≤ 39 ≥ 180
Temp (°C)	36 – 38.4	34 – 35.9 38.5–38.9	32 – 33.9	30 – 31.9 39 – 40.9	≤ 29.9 ≥ 41
Temp (°F)	96.8–101.1	93.1–96.6 101.2–102.0	89.6–93.0	86 – 89.5 102.1–105.6	≤ 85.9 ≥ 105.7
Respiratory rate	12 – 24	10 – 11 25 – 34	6 – 9	35 – 49	≤ 5 ≥ 50
Latest WBC count	3 – 14.9	15 – 19.9	1 – 29 20 – 39.9		< 1 ≥ 40
Acute change in mental status	No	Yes			
SIRS Score (total points)					

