**Table 1 – The Sepsis Screening Score**

This cutoff has a negative predictive value of 96%, which would rule out the majority patients without sepsis. Enrolled patients will be randomized only if they meet criteria for septic shock: 1) hypotension with MAP < 65 mmHg, and 2) evidence of hypoperfusion including lactic acid > 2.2 mmol/L, altered mental status, or decreased urine output of < 0.5 mL/kg in the past hour.

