### Exclusion Criteria:

- Pregnancy
- Prisoners
- Non-survivable traumatic brain injury
- Evidence of ongoing hemorrhage (eg. active gastrointestinal bleed), history of congenital bleeding disorders, therapeutic anticoagulation
- History of congestive heart failure
- Major burns (>20% total body surface area)
- History of adverse reactions to blood product transfusion
- Contraindications to blood transfusions (eg. Jehovah's Witness)
- Contraindications to central venous line and arterial line placement
- Do-Not-Resuscitate or Comfort Care status
- Participation in another interventional study that specifically focuses on sepsis, involves the use of a non-approved product (medication or equipment), or interventions that affect blood coagulation.
- Pending transfer to another unit within the hospital that is not Shock Trauma Intensive Care Unit (STICU) or Medical Intensive Care Unit (MICU).

**Screening and Enrollment:** Patient screening and enrollment will take place at Memorial Hermann Hospital. The research team will screen patients by communicating with the on-call STICU and emergency department (ED) physicians daily to identify patients eligible for enrollment. Hospitalized medical patients on the floor who develop severe sepsis will be identified using the rapid response page, which is already in place to alert the rapid response team of medical floor patients with potential severe sepsis.

[figure not shown]
Enrolled patients will be monitored for up to 72 hours (in time for cultures to result) by the research team for development of septic shock (MAP  $\leq$  65 mmHg and evidence of poor perfusion, such as urine output  $< 0.5$  mL/kg/hr, venous lactic acid  $\geq 2.2$  mmol/L, altered mental status from baseline). Upon meeting these criteria for septic shock, patients will be randomized and immediately started on therapy fluid (either plasma or balanced crystalloids).

Crystalloid administration may already be underway prior to patient randomization. Receiving crystalloids prior to randomization *will not* be an exclusion criterion in this study as long as the total volume received has not met or exceeded 30 mL/kg. The research team will work expeditiously to obtain informed written consent, and once consent has been obtained and patient is randomized, prior fluids will be exchanged for therapy fluid (either plasma or balanced crystalloids).

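### The randomization trigger is stated in two incompatible ways: any one of four signs, or hypotension together with hypoperfusion

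*Combined protocol and SAP*

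**What the plan says.** Enrollment and randomization are separate steps. Under Inclusion Criteria, an adult is enrolled with a Sepsis Screening Score of at least 4 "with a suspected source of infection" and written consent. Four places then say, or imply, when an enrolled patient is randomized.

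- **Inclusion Criteria, bullet list:** "Patients meeting any of the following criteria will be randomized". The bullets are MAP below 65 mmHg, lactic acid above 2.2 mmol/L, altered mental status, and urine output below 0.5 mL/kg in the past hour.
- **Text below Table 1:** "Enrolled patients will be randomized only if they meet criteria for septic shock: 1) hypotension with MAP < 65 mmHg, and 2) evidence of hypoperfusion". The hypoperfusion signs named are "lactic acid > 2.2 mmol/L, altered mental status, or decreased urine output of < 0.5 mL/kg in the past hour".
- **Screening and Enrollment:** enrolled patients are watched for up to 72 hours for low MAP and evidence of poor perfusion. "Upon meeting these criteria for septic shock, patients will be randomized and immediately started on therapy fluid". Here MAP is at or below 65 and lactate at or above 2.2.
- **Study population (Study Design & Methods):** the target is "patients who have sepsis, hypotension with MAP < 65 mmHg, and signs of hypoperfusion such as lactic acid > 2.2 mmol/L", or altered mental status or low urine output.

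The Observational Arm paragraph depends on the same trigger. It takes "Patients with suspected sepsis who do not meet the criteria for randomization", and also those whose consent cannot be obtained within 3 hours.

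**The concern.** The bullet list needs one sign out of four. The other three places need hypotension and a hypoperfusion sign together. The list admits patients whom the text below Table 1 bars, and nothing in the protocol says which prevails.

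Four things are at stake.

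- **Population.** The title, the hypothesis and the target population all concern septic shock. Staff who follow the list could randomize normotensive patients, who would then receive study fluid without the condition the trial is about.
- **Estimate.** Such patients stay in the intention-to-treat analysis. The Statistical Analysis section also plans a per-protocol analysis, and whether these patients were eligible for it would be unclear. With 13 per arm, a few of them matter, and the Sample Size section says the estimates will inform a larger trial.
- **Observational arm.** A looser trigger takes patients out of this arm and a stricter one puts them in, so its make-up changes with the rule applied.
- **Consistency.** Randomization is run by coordinators available around the clock. Different staff could apply different rules to similar patients.

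**Working it through.** The plan gives no figure to reproduce on this point: the Sample Size section states that there is no power analysis. The check is therefore logical, followed by an illustration that rests on stated assumptions.

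**1. Counting sign patterns.** Let H be hypotension, and L, M and U be raised lactate, altered mental status and low urine output. Each is present or absent, so there are 2^4 = 16 patterns.

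- Bullet list: H or L or M or U. All patterns except the empty one qualify: 16 − 1 = 15.
- Text below Table 1: H and (L or M or U). H is fixed as present and at least one of three others is needed: 2^3 − 1 = 7.
- All 7 are among the 15, so the rules disagree on 15 − 7 = 8 patterns: 7 without H but with at least one of L, M and U, and 1 with H alone.

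The count takes the three hypoperfusion signs as a closed list.

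**2. One patient followed through.** Take a patient with a screening score of at least 4, suspected infection, normal blood pressure and altered mental status only. The bullet list randomizes this patient at once. The text below Table 1 forbids it. Screening and Enrollment would keep the patient under observation for up to 72 hours. Altered mental status also scores 1 point in Table 1, so the same sign counts towards enrollment and is then sufficient for randomization.

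**3. Boundary values.** With no altered mental status and normal urine output:

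| MAP (mmHg) | Lactate (mmol/L) | Bullet list | Text below Table 1 | Screening and Enrollment |
|---|---|---|---|---|
| 64 | 2.3 | yes | yes | yes |
| 64 | 2.2 | yes | no | yes |
| 65 | 2.3 | yes | no | yes |
| 65 | 2.2 | no | no | yes |
| 66 | 2.3 | yes | no | no |

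The two conjunctive statements therefore differ from each other at MAP 65 and at lactate 2.2.

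**4. Effect on the estimate (assumed inputs).** Let f be the share of randomized patients without shock, and assume the treatment has no effect in them. The average effect is then (1 − f) times the effect in shock patients, and the expected number of such patients is 26f. If a later trial were sized on the diluted effect with the same standard deviation, its sample size would be multiplied by 1/(1 − f)^2. The protocol gives no value of f.

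| f (assumed) | Patients of 26 | Effect retained | Sample size multiplier |
|---|---|---|---|
| 0 | 0 | 100% | 1.00 |
| 0.10 | 2.6 | 90% | 1.23 |
| 0.25 | 6.5 | 75% | 1.78 |
| 0.50 | 13 | 50% | 4.00 |

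**The case against.** The strongest reply is that the intended rule can be recovered. Three places agree that both elements are needed. The text below Table 1 belongs to the inclusion section and uses limiting language, so the lead-in to the bullets looks like a drafting slip. Patients without shock would be randomized only if staff used the bullets and ignored the rest. This is probably right about intent, and it is why the consequence is put here as something that could happen. It does not remove the conflict, because the slip sits in the list that staff checking eligibility would naturally use.

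Other points stand in part:

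- Pattern counts say nothing about how many patients are affected, and the dilution figures only restate the assumed share. The contradiction rests on neither.
- The list of hypoperfusion signs may be open. The Study population and Screening and Enrollment texts introduce the signs as examples, and the text below Table 1 as items included. The count of 7 depends on reading the list as closed.
- Under the looser rule the 72-hour watch keeps a role for patients who screen positive with none of the four signs. It loses its role only for those who already show one. Mental status gives 1 of the 4 screening points, so it cannot enroll a patient alone.
- The observational arm is mixed under either rule, because it also takes patients whose consent is not obtained in time.
- No formal testing is planned, so no power claim fails. The damage is to the interpretation of the pilot estimates.
- The boundary mismatch matters only at MAP exactly 65 or lactate exactly 2.2. It is secondary.

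**Conclusion.** The concern holds. The protocol contains two operative randomization rules that cannot both be followed, and the one in the formal inclusion list admits patients outside the protocol's own definition of septic shock. The rules disagree on 8 of 15 non-empty sign patterns if the hypoperfusion signs are a closed list. How many of the 26 patients this would affect cannot be derived from the protocol. It could be none if every coordinator applies the conjunctive rule. The figures of about 3 to 13 patients, with 90% to 50% of the effect retained, rest on an assumed 10% to 50% share without shock and no effect in that share. Because this defines who is randomized, it must be corrected even though the correction is small.

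**What to change.** Reconcile the Study population paragraph, the Inclusion Criteria list, the text below Table 1 and the Screening and Enrollment paragraph to one randomization rule. Which rule applies is for the investigators to decide.

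- State the rule once and refer to it elsewhere, with one inequality for MAP and one for lactate, and say whether the hypoperfusion signs are a closed list or examples.
- If the population is to remain septic shock as the protocol itself defines it, reword the lead-in to the bullets so that hypotension and evidence of hypoperfusion are both required, in line with the text below Table 1.
- Define the observational arm by reference to the same rule, keeping late or missing consent as a separate route into it.
- Record which signs were present at randomization, so that eligibility can be verified and the per-protocol population defined.

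The cost is one wording amendment and a matching change to the eligibility form. If the conjunctive rule is kept, accrual may be slower than under the looser list.
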